1.4 Summary of Clinical Experience

In prior clinical experience with MEDI0382 (Cohort 4 of Study D5670C00002), 51 overweight and obese subjects with T2DM were randomized to receive MEDI0382 titrated up from a starting dose of 100 µg to a dose of 200 µg or placebo for up to 41 days. MEDI0382 was shown to have a similar tolerability to marketed GLP-1 receptor agonists, with no significant increases in systolic or diastolic BP observed. Following a mixed-meal tolerance test (MMTT), a least squares (LS) mean for percent change from baseline in glucose area under the concentration-time curve from 0 to 4 hours (AUC_{0-4h}) of -32.78%

(90% confidence interval [90% CI] -36.98, -28.57) was observed in MEDI0382-treated subjects versus -10.16% (90% CI -14.10, -6.21) in placebo-treated subjects ($p < 0.0001$). A LS mean change from baseline in body weight of -3.84% (90% CI -4.55, -3.12) was observed in MEDI0382-treated subjects versus -1.70% (90% CI -2.40, -1.01) in placebo-treated subjects ($p < 0.001$). In the same study (D5670C00002), doses of 300 μg were studied for 7 days in 2 separate cohorts, each exploring different uptitration schedules to reach this dose. The tolerability and efficacy profiles were similar to that observed in previous cohorts.

The combination of MEDI0382 with dual therapy of dapagliflozin and metformin has not been studied previously. However, given the commercial availability of dapagliflozin, this drug (and other SGLT2 inhibitors) will likely be a concomitant medication in future Phase 3 clinical studies of MEDI0382. Because the 2 agents exert their glyceemic and weight-lowering effects via different mechanisms, the coadministration of the 2 compounds is expected to show improved effects on glyceemic control and body weight as well as positive effects on BP (due to renal sodium loss driven by both SGLT2 inhibition and glucagon) compared to the oral, dual therapy of dapagliflozin and metformin given alone.

Given the likelihood of concomitant administration of MEDI0382 with SGLT2 inhibitors and metformin in the ongoing clinical development program, this exploratory study aims to (a) explore the efficacy and safety profile associated with the combination of MEDI0382 and dual therapy of SGLT2 inhibitor (dapagliflozin) and metformin and (b) characterize the profile of glyceemic and metabolic control following administration of the triple combination therapy versus oral, dual-combination therapy.

1.5 Rationale for Conducting the Study

This is an exploratory Phase 2a efficacy study designed to investigate the effects on glyceemic control and the safety profile associated with MEDI0382 titrated up to a dose level of 300 μg when coadministered with dapagliflozin and metformin in subjects with T2DM with a body mass index (BMI) of $\geq 25 \text{ kg/m}^2$ to $\leq 40 \text{ kg/m}^2$ and a HbA1c of $\geq 7.0\%$ to $\leq 10.0\%$. The results of this study will provide additional information about the efficacy, safety, tolerability, and pharmacokinetic (PK) profile of MEDI0382 in the likely intended clinical T2DM population.

Previous clinical experience with another GLP-1 monoagonist (exenatide) coadministered with dapagliflozin demonstrated that the combination resulted in significant reductions in HbA1c, FPG, weight, and systolic BP compared to either agent alone on a background of metformin (Frías et al, 2016). Therefore, the simultaneous administration of MEDI0382 with dapagliflozin is expected to show superior effects on glyceemic control, body weight, and BP.

SGLT2 inhibitors have emerged as an effective therapy for glucose control and are likely to be a concomitant medication for subjects in the ongoing development program for MEDI0382. In addition, prior to including such subjects in Phase 3 studies, it is important to study the safety profile of MEDI0382 when given in combination with a SGLT2 inhibitor.

1.6 Benefit-risk and Ethical Assessment

The study will be performed in accordance with ethical principles that have their origin in the Declaration of Helsinki and are consistent with International Council for Harmonization (ICH)/Good Clinical Practice (GCP) and applicable regulatory requirements.

MEDI0382 is a GLP-1 and glucagon receptor coagonist that promotes glucose lowering and weight loss and is targeted at subjects with T2DM. MEDI0382 has the potential to deliver improvements in glycemic control and lipid homeostasis, and it is predicted to be a useful therapy for T2DM.

The study design aims to minimize potential risks to subjects participating in this study based on the proposed inclusion/exclusion criteria, safety monitoring, and uptitration dosing schedule. Euglycemic diabetic ketoacidosis (eDKA) and hypovolemia are rare potential risks in subjects taking SGLT2 inhibitors. All subjects will be monitored throughout the study to ensure adequate glycemic control, ketones production, and intravascular volume status. Subjects will be given appropriate training in subcutaneous (SC) injection administration as well as use of any devices. Refer to the current MEDI0382 IB and dapagliflozin IB for further information on the potential benefits of MEDI0382 and dapagliflozin and an assessment of the potential and known risks. Identified risks for this study include nausea and vomiting. Potential risks for this study include hypoglycemia, volume depletion, and diabetes ketoacidosis (DKA).

1.6.1 Nausea and Vomiting

If a subject experiences nausea and vomiting in relation to the investigational product, in the first instance, conservative measures should be advised including reducing meal size and maintaining adequate hydration. When necessary, if there is persistent vomiting, a subject may be given an antiemetic to control his/her symptoms; a 5HT₃ receptor antagonist (eg, ondansetron) or cyclizine is preferable in this situation rather than antiemetics, which may affect gastric emptying, and in particular dopamine receptor antagonists (eg, metoclopramide or domperidone).

1.6.2 Hypoglycemia

A hypoglycemic event is considered severe if associated with severe cognitive impairment requiring external assistance for recovery as defined by the American Diabetes Association. Spontaneous and clinically significant hypoglycemia defined as blood glucose < 54 mg/dL [3.0 mmol/L] with or without symptoms ([Skyder et al, 2017](#)) has not been seen in prior studies with MEDI0382 (up to a dose of 300 µg) alongside metformin. In addition, no episodes of major and minor hypoglycemia were reported in a randomized control study evaluating the efficacy and safety of exenatide (a GLP-1 monoagonist) in combination with dapagliflozin on a background of metformin ([Frías et al, 2016](#)). Furthermore, the mechanism of action of dapagliflozin (SGLT2 inhibition) does not interfere with normal endogenous glucose production in response to hypoglycemia and does not stimulates insulin release. Therefore, the risk of hypoglycemia in this study is considered low. However, all subjects will be provided with a diary and a glucometer and will be advised to check their capillary blood glucose level if they have symptoms of hypoglycemia (hunger, dizziness, shaking, sweating, or irritability) or feel unwell and will be expected to record the blood glucose level in their diary and contact the study team immediately. Management of the event should be as per standard local protocols. Hypoglycemia episodes should be documented as an adverse event (AE). Pharmacological treatments administered for hypoglycemia (eg, dextrose/glucose tablets, glucagon) should be recorded in the electronic case report form (eCRF) as concomitant medications.

1.6.3 Volume Depletion

MEDI0382 treatment with doses of up to 300 µg has been associated with a reduction in BP compared to baseline (-2.26 mmHg for diastolic BP and -8.49 mmHg for systolic BP) as estimated by ambulatory blood pressure monitoring (ABPM).

GLP-1 receptor agonist augment renal sodium excretion ([Tonnejck et al, 2016](#)). The mechanism by which a GLP-1 receptor agonist increase renal excretion is not well understood, but it includes vasodilation and possibly a direct effect on the renal tubule. ([DeFronzo, 2017](#)).

Dapagliflozin causes glucosuria and a subsequent mild osmotic diuretic effect and decreased intravascular volume. Due to its mechanism of action, dapagliflozin increases diuresis associated with a modest decrease in BP, which could be more pronounced in patients with very high blood glucose concentrations. Refer to the current dapagliflozin IB for more information on this risk.

The combined sodium loss and the potential tolerability risk (vomiting) resulting from GLP-1 on a background of dapagliflozin raises a theoretical risk of higher incidence of symptomatic hypovolemia in subjects given both products in combination.

During the course of this study, the subject volume status will be closely monitored at each visit by assessing vital signs with BP (including lying and standing measurements). In addition, an ABPM device will be used during inpatient and outpatient visits.

Subjects will be advised to maintain adequate fluid intake throughout the study and to contact the study team if they experience dizziness or feel unwell. Management of volume depletion events should be as per standard local protocols.

Any episodes of symptomatic volume depletion (eg, hypotension, dehydration, or syncope) should be recorded as an AE.

1.6.4 Diabetic Ketoacidosis/Euglycemic Ketoacidosis

The glucagon component of MEDI0382 may lead to an increase in ketone production due to the potential increased oxidation of free fatty acid (FFA). It is also hypothesized that SGLT2-induced glycosuria predisposes subjects to increased ketogenesis (Qiu et al, 2017). Therefore, the combination of MEDI0382 and dapagliflozin (or any other SGLT2 inhibitor) might theoretically increase the risk to ketosis. In MEDI0382 clinical studies to date, there have been no cases of ketoacidosis (either hyper- or euglycemic cases).

Diabetes ketoacidosis, sometimes with normal glucose levels (ie, eDKA), has been reported very rarely in patients taking SGLT2 inhibitors (canagliflozin, dapagliflozin, or empagliflozin) in postmarketing surveillance (Rosenstock and Ferrannini, 2015). The clinical risk of developing DKA upon concomitant use of MEDI0382 and dapagliflozin is deemed very low. However, adequate monitoring will be implemented as described below to minimize the risk to study subjects.

During the course of the study, subjects will test their blood ketone level daily using ketone finger-prick testing strips and ketone monitor provided. In addition, subjects will be supplied with a paper diary, which will be reviewed by study staff at each visit. Subject will test their capillary ketone bodies every day before breakfast. Furthermore, subjects will be advised to check their blood for the presence of ketones and check their blood glucose using finger-prick testing with a glucometer if they experience any of the symptoms listed below and/or during acute illness.

Subjects will be instructed to contact the site immediately if the results indicate the presence of ketonemia (> 3 mmol/L), and/or elevated glucose levels (> 140 mg/dL [> 7.8 mmol/L]), and/or experience the following symptoms:

- Polyuria or polydipsia
- Malaise, generalized weakness, or fatigability
- Nausea and vomiting—may be associated with diffuse abdominal pain, decreased appetite, and anorexia
- Altered consciousness (eg, mild disorientation, confusion)

At the unit, the investigator should assess and determine whether the subject is at risk to develop ketoacidosis or is progressing towards ketoacidosis based on the subject's medical history, physical examination, and supportive laboratory results. The investigator should then determine whether the subject can be treated at the unit or should be referred to the local hospital for further evaluation and treatment of DKA.

The diagnosis of DKA will be made if the following are seen:

- Plasma glucose > 250 mg/dL (> 13.9 mmol/L)
- Increased anion gap metabolic acidosis (> 10 - 12 mEq/l) associated with pH < 7.30 and bicarbonate level < 18 mEq/l
- Elevated plasma ketone levels (> 3.0 mmol/L)

The diagnosis of eDKA will be made if the subject has the following:

- Increased anion gap metabolic acidosis as outlined above
- Elevated plasma ketones with plasma glucose < 250 mg/mL

However, any subject with a pH of < 7.35 associated with ketones > 3.0 mmol/L (regardless of glucose levels) may be considered to be progressing towards ketoacidosis. Therefore, such subjects should be discontinued from the study (Section 4.1.6) and monitored closely per local protocols.

Any event of DKA or eDKA should be managed according to standard local protocols.

In reporting DKA events, it is important to distinguish ketosis from DKA. Low levels of ketosis, in which blood or urine ketone values are elevated, can occur in individuals who follow a low-carbohydrate, high-fat diet or after prolonged periods of fasting. Ketosis is a

benign condition if symptoms are absent and the blood pH remains within normal limits (ie, no acidosis). In contrast, a DKA episode may be confirmed when a subject has potential symptoms of DKA as described above, elevated blood/urine ketone values, metabolic acidosis (characterized by low arterial blood pH, decreased serum bicarbonate, and an increased anion gap), and hyperglycemia (although some individuals may have normal or only mildly elevated blood glucose levels).

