4.1.6 Discontinuation of Investigational Product

An individual subject will not receive any further investigational product if any of the following occur in the subject:

1. Withdrawal of consent from further treatment with investigational product or lost to follow up
2. An AE that in the opinion of the investigator or the sponsor warrants discontinuation from further dosing
3. Subject is determined to have met one or more of the exclusion criteria or failed to meet all of the inclusion criteria for study participation at study entry, and at the decision of the investigator, continuing of investigational product might constitute a safety risk.
4. Subject noncompliance that in the opinion of the investigator or sponsor warrants withdrawal (eg, refusal to adhere to scheduled visits)
5. Pregnancy in a female subject
6. Evidence of ketoacidosis or progression to ketoacidosis, ie, blood ketones (β -hydroxybutyrate) > 3.0 mmol/l and pH $< 7.35 \pm$ serum bicarbonate < 18 mmol/L in conjunction with clinical symptoms. The presence of elevated plasma glucose is not required as part of this diagnosis. The investigator should consider interrupting dapagliflozin temporarily if DKA is suspected. The subject should be promptly evaluated. If DKA is confirmed, dapagliflozin should be discontinued permanently.
7. Hypoglycemia events: Subjects should discontinue investigational product if they experience severe hypoglycemia as define by the American Diabetes Association
 - Requiring assistance of another person to actively administer carbohydrates, glucagon, or take other corrective actions
 - Plasma glucose concentrations may not be available during an event, but neurological recovery following the return of plasma glucose to normal is considered sufficient evidence that the event was induced by a low plasma glucose concentration
8. Kidney disorders as determine by a decrease in renal function that would preclude continued treatment with metformin according to local guidance
9. Hepatic disorders: subjects with central laboratory ALT and/or AST $> 3 \times$ ULN will be scheduled for a follow-up visit within 3 days following the receipt of the results. Subjects should be discontinued from receiving investigational product if initial and repeat laboratory tests meet any of the following:
 - ALT and/or AST are $3 \times$ ULN and TBL $> 2 \times$ ULN
 - ALT and/or AST are $5 \times$ ULN for 14 consecutive days, at any time after initial confirmatory results.

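### Section 1.6.4 takes a subject progressing towards ketoacidosis out of the study, while the section it cites stops product only and, on its natural reading, also requires symptoms

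*Protocol*

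**What the plan says.** **Protocol Section 1.6.4.** At the unit, "the investigator should assess and determine whether the subject is at risk to develop ketoacidosis or is progressing towards ketoacidosis", using history, examination and laboratory results. After the criteria for DKA and euglycemic DKA (eDKA), the section adds a wider category: any participant showing a "pH of < 7.35 associated with ketones > 3.0 mmol/L (regardless of glucose levels) may be considered to be progressing towards ketoacidosis". The action follows: "such subjects should be discontinued from the study (Section 4.1.6", with close monitoring under local protocols. The section later calls ketosis a "benign condition if symptoms are absent and the blood pH remains within normal limits (ie, no acidosis". The eDKA glucose limit is printed as below 250 mg/mL; the DKA limit just above it is 250 mg/dL (13.9 mmol/L).

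**Protocol Section 4.1.6.** The heading and lead-in concern investigational product. Item 6 is titled "Evidence of ketoacidosis or progression to ketoacidosis". It sets ketones above 3.0 mmol/L and pH below 7.35, then a plus-or-minus sign, then "serum bicarbonate < 18 mmol/L in conjunction with clinical symptoms". The next sentence reads "The presence of elevated plasma glucose is not required as part of this diagnosis". Item 2 is a judgement-based stop: "An AE that in the opinion of the investigator or the sponsor warrants discontinuation from further dosing". The closing paragraph asks sites to keep subjects who stop product in the study, with all other procedures, to its scheduled end. It makes exceptions for withdrawn consent, loss to follow-up, alternative treatment and enrolment in another study.

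**The concern.** Section 1.6.4 sends the reader to 4.1.6, so the two should give one instruction. They differ in two ways.

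- **What stops.** One section ends study participation; the other ends dosing and keeps the subject under study assessment. A subject removed from the study before Day 28 leaves the scheduled follow-up and has no Day 28 mixed-meal tolerance test (MMTT), and so no primary endpoint value.
- **Who stops.** Section 1.6.4 names two laboratory limits, waives glucose and is silent on symptoms. Item 6 covers the same category with the same limits but mentions symptoms. By the protocol's own description, low pH takes a subject outside benign ketosis even without symptoms, so this is a case on which the stopping rule should be clear.

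Ketosis is the theoretical risk that the protocol itself attaches to combining MEDI0382 with an SGLT2 inhibitor.

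**Working it through.** **Step 1: the two rules side by side**

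| Element | Section 1.6.4 | Section 4.1.6, item 6 |
|---|---|---|
| Category | Progressing towards ketoacidosis | Ketoacidosis or progression to it |
| pH | < 7.35 | < 7.35 |
| Ketones | > 3.0 mmol/L | > 3.0 mmol/L |
| Glucose | Any | Elevation not required |
| Bicarbonate | Not in the stop sentence | < 18 mmol/L, optional |
| Symptoms | Not mentioned in the stop sentence | Mentioned, after the bicarbonate term |
| What stops | Study participation | Investigational product |

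**Step 2: how far the triggers differ.** Take four yes/no facts: K (ketones > 3.0), P (pH < 7.35), B (bicarbonate < 18) and S (symptoms). They give 2^4 = 16 combinations.

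- Section 1.6.4 stops when K and P hold.
- Item 6, natural reading (symptoms apply to the whole criterion): K, P and S. This reading is natural because the following sentence waives glucose and waives nothing else.
- Item 6, narrow reading (symptoms attach only to the optional bicarbonate term): K and P.

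On the natural reading the rules disagree when K and P hold without S, whatever B is: 2 of 16 combinations. On the narrow reading they disagree in 0 of 16. These are counts of combinations, not of subjects. As an illustration, pH 7.32 with ketones 3.5 mmol/L and no symptoms meets 1.6.4 but does not meet item 6 on the natural reading.

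**Step 3: what the difference in action costs.** This difference does not depend on how item 6 is parsed.

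- Under 4.1.6 the subject remains scheduled for the Day 28 MMTT and the follow-up visits 14 and 28 days after the last dose.
- A subject who discontinues the study gets the visit in Section 4.2.4.1. Its legible items include no MMTT, pH or ketone measurement. The chemistry panel does include bicarbonate (Section 4.3.3).
- SAP Section 3.4.1.2 does not impute the primary endpoint, because there is only one post-baseline value. SAP Section 3.1 bars carrying baseline forward. A subject without the Day 28 MMTT therefore contributes nothing to the primary comparison.

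One such subject is 1/23 = 4.3% of an arm. For power, the plan's standardized difference is 30/20 = 225/150 = 1.5. By the normal approximation, with critical value 1.960:

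- 23 and 23 subjects: 1.5 × √(23 × 23/46) = 5.087, so power is Φ(5.087 − 1.960) = 99.9%, consistent with the plan's figure of more than 95%.
- 22 and 23 subjects: 1.5 × √(22 × 23/45) = 5.030, so power is Φ(5.030 − 1.960) = 99.9%.

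The loss is one of safety information and completeness, not of power.

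**Step 4: the unit.** 250 mg/mL × 100 mL/dL = 25,000 mg/dL, which is 100 times the DKA limit. It is a misprint for mg/dL.

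**The case against.** The other side has several fair points.

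- **Both rules can be obeyed.** Section 4.1.6 lists when product must stop; it does not say that dosing must continue otherwise. A site that stops an asymptomatic subject under 1.6.4 breaches nothing, and item 2 allows the same stop by judgement. This stands. A reader might infer that 4.1.6 requires such a subject to keep dosing, but it does not. What remains is that a site working from 4.1.6 alone has only a discretionary route.
- **Section 1.6.4 leaves judgement.** It opens with an investigator assessment, and its category is worded as a possibility. This also stands, although the action sentence is directive.
- **The symptom conflict depends on parsing.** Correct: on the narrow reading it disappears. A stopping rule should not rest on where a clause attaches.
- **The cross-reference shows what was meant.** Because 1.6.4 cites the section on discontinuing product, a product stop is the likely intention. The documents therefore do not support inferring that the sponsor wanted these subjects out of the study. The printed instruction still says so.
- **Follow-up might end anyway.** Section 4.1.6 releases a subject who starts alternative treatment, and 1.6.4 keeps close monitoring under local protocols. Both limit the loss without reconciling the text.
- **The affected group is very small.** The symptom list in 1.6.4 is broad, and the protocol reports no ketoacidosis with MEDI0382 to date.

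A reader might also size the problem by the days without a scheduled pH or by the doses remaining after each pH sample. Those figures describe monitoring, which is the same under either rule and unchanged by the fix.

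**Conclusion.** The inconsistency is real and minor. The firm part is the action: 1.6.4 ends study participation where 4.1.6 ends dosing only, on any reading. Followed literally before Day 28, 1.6.4 costs that subject's scheduled follow-up and primary endpoint value. The weaker part is the trigger: on the natural but not the only reading of item 6, an asymptomatic subject over both limits meets one rule and not the other.

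The documents give no frequency for this event. The minor rating rests on the protocol's own judgement that the DKA risk is very low and on its report of no cases. The mg/mL limit is a plain unit error, unlikely to mislead because the correct unit stands just above it.

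**What to change.** 1. In Section 1.6.4, direct that these subjects be discontinued from investigational product, with follow-up per Section 4.1.6, in place of discontinuation from the study.
2. In Section 4.1.6, item 6, use the limits that 1.6.4 already states: pH < 7.35 with ketones > 3.0 mmol/L, and say expressly that neither elevated glucose nor symptoms are required.
3. Keep the dapagliflozin instructions in item 6 as they are: consider interruption if DKA is suspected, and stop permanently if it is confirmed.
4. Correct the eDKA glucose limit to < 250 mg/dL (< 13.9 mmol/L).

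This is protocol wording only, with no new visits, tests or subjects. The downside is that a rare asymptomatic subject over both limits would stop dosing. The documents do not settle whether the sponsor meant symptoms to be required, so the second change is a clinical choice for the sponsor to confirm. If symptoms are to be required, both sections should say so.
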